5.5.3.2.2 Expansion phase

TG02 dose reductions and skipped dose(s) are allowed in any cycle. A “skipped dose” for TG02 means that one or more single doses will be omitted and not replaced, in order not to change the temporal relationship.

For example, if TG02 is planned on days 1, 4, 8 but day 4 has to be omitted, TG02 can be restarted on day 8 if the AE is sufficiently resolved: TG02 is always restarted on a scheduled dose day.

Toxicities possibly related to TG02 should be managed as outlined in the tables below.

NOTE: * in below tables: There will be no dose reductions below 100 mg TG02 BIW

Group A: TG02-related Hematological Adverse Events

Adverse Event	Action to be taken with TG02
Thrombocytopenia	
First occurrence of grade 3 without bleeding	Skip one or more doses of TG02 until improved to grade ≤ 1 . Re-introduce TG02 at initial dose.
Recurrence of the same grade 3 event without bleeding	Skip one or more doses of TG02 until improved to grade ≤ 1 . Re-introduce TG02 at a reduced dose* If TG02 has been re-introduced after a second event and the event recurs, consider the individual benefit versus the risk of continuing TG02. If TG02 is re-introduced, re-introduce at a reduced dose * If TG02 has been re-introduced after a third event and the event recurs, discontinue TG02.
First occurrence of grade 3 with bleeding or grade 4 event	Skip one or more doses of TG02 until improved to grade ≤ 1 . Re-introduce TG02 at a reduced dose *
Recurrence of the same grade 3 event with bleeding	Skip one or more doses of TG02 until improved to grade ≤ 1 . Consider the individual benefit versus the risk of continuing TG02. If TG02 is re-introduced, re-introduce at a reduced dose * If TG02 has been re-introduced after a second event and the event recurs, discontinue TG02.

Adverse Event	Action to be taken with TG02
Recurrence of the same grade 4 event	Discontinue TG02.
Anemia	
First occurrence of grade 3 event	Skip one or more doses of TG02 until improved to grade ≤ 2 . Re-introduce TG02 at initial dose.
Recurrence of the same grade 3 event	Skip one or more doses of TG02 until improved to grade ≤ 2 . Re-introduce TG02 at a reduced dose*. If TG02 has been re-introduced after a second event and the event recurs, discontinue TG02.

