Grade 4 event	Skip one or more doses of TG02 until improved to grade ≤ 1 . Consider the individual benefit versus the risk of continuing TG02. If TG02 is re-introduced, re-introduce at a reduced dose*. If TG02 has been re-introduced after a second event and the event recurs, discontinue TG02.
Recurrence of the same grade 4 event	Discontinue TG02.
Neutropenia	
First occurrence of grade 3 event	Skip one or more doses of TG02 until improved to grade ≤ 1 . Re-introduce TG02 at a reduced dose *
Recurrence of the same grade 3 event	Skip one or more doses of TG02 until improved to grade ≤ 1 . Re-introduce TG02 at a reduced dose * If TG02 has been re-introduced after a second event and the event recurs, consider the individual benefit versus the risk of continuing TG02. If TG02 is re-introduced, re-introduce TG02 at a reduced dose *. If TG02 has been re-introduced after a third event and the event recurs, discontinue TG02.
Grade 4 event	Skip one or more doses of TG02 until improved to grade ≤ 1 . Re-introduce TG02 at a reduced dose *.
Recurrence of the same grade 4 event	Discontinue TG02.
Febrile Neutropenia	
Grade 3 or 4 event	Skip one or more doses of TG02 until fever is resolved and neutropenia is improved to grade ≤ 1 . Re-introduce TG02 at a reduced dose *

Adverse Event	Action to be taken with TG02
Recurrence of the same grade 3 event	Skip one or more doses of TG02 until improved to grade ≤ 1 . Consider the individual benefit versus the risk of continuing TG02. If TG02 is re-introduced, re-introduce TG02 at a reduced dose *. If TG02 has been re-introduced after a second event and the event recurs, discontinue TG02.
Recurrence of the same grade 4 event	Discontinue TG02.

Group A: TG02-related Non-hematologic Adverse Events

Adverse Event	Action to be taken with TG02
Nausea/ Vomiting	
Grade 1 or 2 event	Manage with moderate anti-emetic treatment until improved to grade ≤ 1 . Prophylaxis should be given before TG02 dosing (see Section 5.6.2). If a patient experiences persistent or recurrent grade 2 nausea/vomiting that do not improve to grade ≤ 1 with maximal supportive measures within 3 days, then TG02 dosing should be skipped until improved to grade ≤ 1 . The dose of TG02 may be reduced *

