Second occurrence of grade 3 event with bleeding or grade 4 event occurring on Day -7 to Day -1 of cycle	
Skip one or more doses of TG02 until improved to grade ≤ 1. If improved to grade ≤ 1 by Cycle 1 Day 1, initiate TMZ at initial dose. Consider the individual benefit versus the risk of continuing TG02. If TG02 is re-introduced, re-introduce at a reduced dose *.
 
If TG02 has been re-introduced after a third event and the event recurs, discontinue TG02.

First occurrence of grade 3 event with bleeding or grade 4 event occurring on Day 1 to Day 7 of cycle	
Skip one or more doses of TG02 and interrupt TMZ until improved to grade ≤ 1. Consider the individual benefit versus the risk of continuing TMZ:
 
 • If TMZ is re-introduced, re-introduce TMZ and TG02 at a reduced dose *. • If TMZ is discontinued, continue TG02 at the same or a reduced dose * bi-weekly (on Days 1, 4, 8, 11, 15, 18, 22, 25) of a 28-day schedule.
Second occurrence of grade 3 event with bleeding or grade 4 event occurring on day 1 to Day 7 of cycle	
Skip one or more doses of TG02 and interrupt TMZ (if TMZ was re-introduced after the first event) until improved to grade ≤ 1. Re-introduce TG02 at a reduced dose *. Discontinue TMZ.
 
If TG02 has been re-introduced after a second event and the event recurs, consider the individual benefit versus the risk of continuing TG02. If TG02 is re-introduced, re-introduce at a reduced dose *.
 
If TG02 has been re-introduced after a third event and the event recurs, discontinue TG02.

Adverse Event	Action to be taken with TG02/ TMZ
Grade 3 or 4 event occurring on Day 21 – Day 28 of cycle	Skip one or more doses of TG02 and TMZ until improved to grade ≤ 1 . Re-introduce TG02 at initial dose and re-introduce TMZ at a reduced dose.
Recurrent grade 4 event occurring on Day 21 – Day 28 of cycle	Discontinue TMZ. Consider the individual benefit versus the risk of continuing TG02. If TG02 is continued, continue TG02 at the same or a reduced dose * bi-weekly (on Days 1, 4, 8, 11, 15, 18, 22, 25) of a 28-day schedule. Alternatively, discontinue TG02 and rechallenge with TMZ at lower dose.
Grade 3 or 4 event that does not improve to grade ≤ 2 within 28 days	Discontinue patient from study.
Anemia (TMZ decision as per local practice)	
First occurrence of grade 3 event	Skip one or more doses of TG02 until improved to grade ≤ 2 . Re-introduce TG02 at initial dose.

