Recurrence of the same grade 3 event	Skip one or more doses of TG02 until improved to grade ≤ 2 . Re-introduce TG02 at reduced dose *. If TG02 has been re-introduced after a second event and the event recurs, discontinue TG02.
Grade 4 event	Skip one or more doses of TG02 until improved to grade ≤ 1 . Consider the individual benefit versus the risk of continuing TG02 at reduced dose *. If TG02 is re-introduced, re-introduce at a reduced dose *.
Recurrence of the same grade 4 event	Discontinue TG02.
Neutropenia	
First occurrence of grade 3 event	Skip one or more doses of TG02 and interrupt TMZ until improved to grade ≤ 1 . Re-introduce TG02 at a reduced dose * and TMZ at initial dose.

Adverse Event	Action to be taken with TG02/ TMZ
Recurrence of the same grade 3 event	
Skip one or more doses of TG02 and interrupt TMZ until improved to grade ≤ 1. Re-introduce TG02 * and/ or TMZ at a reduced dose.
 
If TG02 and TMZ have been re-introduced after a second event and the event recurs, consider the individual benefit versus the risk of continuing TG02 or TMZ:
 
 • Discontinue TMZ. Continue TG02 at the same or a reduced dose *bi-weekly (on Days 1, 4, 8, 11, 15, 18, 22, 25) of a 28-day schedule. • Alternatively, discontinue TG02 and continue TMZ at a reduced dose. 
If TG02 or TMZ has been re-introduced after a second event and the event recurs, discontinue TG02 and TMZ.

Grade 4 event	Skip one or more doses of TG02 and TMZ until improved to grade ≤ 1 . Re-introduce TG02 * and TMZ at a reduced dose.
Recurrence of the same grade 4 event	Discontinue TG02. TMZ dosing as per local practice.
Febrile Neutropenia	
Grade 3 or 4 event	Skip one or more doses of TG02 and interrupt TMZ until fever is resolved and neutropenia is improved to grade ≤ 1 . Re-introduce TG02 * and TMZ at a reduced dose.
Recurrence of the same grade 3 event	
Skip one or more doses of TG02 and interrupt TMZ until fever is resolved and neutropenia is improved to grade ≤ 1. Consider the individual benefit versus the risk of continuing TG02 or TMZ:
 
 • Discontinue TMZ. Continue TG02 at the same or a reduced dose * bi-weekly (on Days 1, 4, 8, 11, 15, 18, 22, 25) of a 28-day schedule. • Alternatively, discontinue TG02 and continue TMZ at a reduced dose. 
If TG02 or TMZ has been re-introduced after a second event and the event recurs, discontinue TG02 and TMZ.

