Grade 4 event	Skip one or more doses of TG02 until improved to grade ≤ 1 . Consider the individual benefit versus the risk of continuing TG02. If TG02 is re-introduced, re-introduce at a reduced dose*. If TG02 has been re-introduced after a second event and the event recurs, discontinue TG02.
Recurrence of the same grade 4 event	Discontinue TG02.
Neutropenia	
Occurrence grade 3 event	Skip one or more doses of TG02 until improved to grade ≤ 1 . Re-introduce TG02 at a reduced dose *.
Grade 4 event	Skip one or more doses of TG02 until improved to grade ≤ 1 . Re-introduce TG02 at a reduced dose*.
Febrile Neutropenia	
Grade 3 or 4 event	Skip one or more doses of TG02 until fever is resolved and neutropenia is improved to grade ≤ 1 . Re-introduce TG02 at a reduced dose *.
Recurrence of the same grade 4 event	Discontinue TG02.

Group C: TG02-related Non-hematologic Adverse Events

Adverse Event	Action to be taken with TG02
Nausea/ Vomiting	
Grade 1 or 2 event	Manage with moderate anti-emetic treatment until improved to grade ≤ 1 . Prophylaxis should be given before TG02 dosing (see Section 5.6.2). If a patient experiences persistent or recurrent grade 2 nausea/vomiting that do not improve to grade ≤ 1 with maximal supportive measures within 3 days, then TG02 dosing should be skipped until improved to grade ≤ 1 . The dose of TG02 may be reduced*.
Grade 3 nausea Grade 3 or 4 vomiting	Skip one or more doses of TG02 until improved to grade ≤ 1 . If improved to grade ≤ 1 in <48 hours, re-introduce TG02 at the initial dose. If not improved to grade ≤ 1 with maximal supportive measures within 48 hours, re-introduce TG02 at a reduced dose *. Continue prophylaxis and management with at least moderate anti-emetic treatment (see Section 5.6.2).

Adverse Event	Action to be taken with TG02
Diarrhea	
Grade 1 or 2 event	
Manage with anti-diarrheal treatment until improved to grade ≤ 1. Prophylaxis should be given before TG02 dosing (see Section 5.6.2).
 
If a patient experiences persistent or recurrent grade 2 diarrhea that does not improve to grade ≤ 1 with maximal supportive measures within 3 days, then TG02 dosing should be skipped until improved to grade ≤ 1. The dose of TG02 may be reduced*.
 
Continue prophylaxis and management with anti-diarrheal treatment (see Section 5.6.2).

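### TG02 stopping instructions need three edits: grade 4 anemia rows in Groups A and C, one neutropenia cell in Group B, and an asterisk note that omits the stop at 100 mg

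*Combined protocol and SAP*

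**What the plan says.** **General rule.** Section 5.5.3.1 applies to all groups. It lists two TG02 doses, 150 and 100 mg, and sets 100 mg as the floor. A patient whose starting or current dose is 100 mg, and who has a toxicity for which the tables require a reduction, is discontinued from study treatment. Sites unsure about the tables are told to contact the Sponsor.

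**Asterisk note.** The note above each group's tables (5.5.3.2.2, 5.5.3.3.3, 5.5.3.4) repeats the floor. It does not mention discontinuation.

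**Grade 4 anemia.** In Group A the first-event row ends: if TG02 is resumed, "re-introduce at a reduced dose*. If TG02 has been re-introduced after a second event and the event recurs, discontinue TG02". The row below, headed "Recurrence of the same grade 4 event", says to discontinue. Group C's grade 4 row also contains "If TG02 has been re-introduced after a second event and the event recurs, discontinue TG02", again followed by a row that stops TG02 at recurrence. Group B's grade 4 row says "Consider the individual benefit versus the risk of continuing TG02 at reduced dose" and does not have the extra sentence.

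**Group B, recurrent grade 3 neutropenia (5.5.3.3.3).** TG02 and/or TMZ is resumed at a lower dose. If both were resumed after a second event and it recurs, the site chooses one drug to keep. The last sentence says that if TG02 or TMZ was resumed after a second event and it recurs, both are stopped.

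**Late stops.** Several rows defer the stop. Group A grade 3 neutropenia, for example, ends with "If TG02 has been re-introduced after a third event and the event recurs, discontinue TG02".

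**The concern.** These are the instructions a site follows when a severe toxicity repeats. Grade 3 or 4 neutropenia and liver enzyme elevation were the events behind the dose cuts described in 1.3.3.2. If a table cell disagrees with the next row, or seems to allow another course at 100 mg where the general rule says stop, two sites can treat the same event differently. A site working from the table and its note alone can read a reduced-dose entry combined with the 100 mg floor as permission to resume at 100 mg. At stake are patient safety and uniform treatment across sites; no test statistic or sample size is involved.

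**Working it through.** The plan states no figure on this point. The check sets the rows side by side and then traces repeated occurrences of the same event against 5.5.3.1.

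**1. Grade 4 anemia, Groups A and C.**
- First event: resume, if at all, at a reduced dose. From 150 mg that means 100 mg.
- Second event, by the next row: stop.
- Second event, by the extra sentence: resumption is contemplated, with the stop at the third event.
- Second event, by 5.5.3.1: the patient is at 100 mg and no lower dose exists, so stop.

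In the recurrent grade 3 anemia row of Group A the same closing sentence fits: "Re-introduce TG02 at a reduced dose*. If TG02 has been re-introduced after a second event and the event recurs, discontinue TG02". That row starts at the second event and has no later row to contradict it. The sentence appears to have been carried over into the grade 4 row.

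**2. Group B, recurrent grade 3 neutropenia.** Recurrence after resumption following a second event leads to one drug kept in one sentence and to both stopped in another. In the cell for recurrent grade 3 thrombocytopenia without bleeding, the matching last sentence refers to a third event and the order is coherent. In the cell for recurrent grade 3 febrile neutropenia, the second-event wording also works, because there the choice of a single drug is already made at the second event. The neutropenia cell fits neither pattern.

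**3. Reduced-dose entries after a reduction has already been made.** Convention: start at 150 mg, the same event recurs, only one reduction (150 to 100) is possible, and each later entry giving a reduced TG02 dose is counted. Entries for which reduction is optional or the same dose is allowed are left out.

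| Sequence | Table stops at event | 5.5.3.1 stops at event | Later entries |
|---|---|---|---|
| A: thrombocytopenia G3, no bleeding | 4 | 3 | 1 |
| A: thrombocytopenia G3, bleeding | 3 | 2 | 1 |
| A: neutropenia G3 | 4 | 2 | 2 |
| A: febrile neutropenia G3 | 3 | 2 | 1 |
| A: other non-hematologic G3 | 4 | 3 | 1 |
| A: other non-hematologic G4 | 3 | 2 | 1 |
| C: the same two thrombocytopenia and two non-hematologic sequences | as in A | as in A | 4 |
| B: thrombocytopenia, Day -7 to -1 | see below | 2 | 1 |
| B: thrombocytopenia, Day 1 to 7, TMZ resumed | 4 | 2 | 2 |
| B: neutropenia G3 | unclear (item 2) | 2, if TG02 is the drug reduced | 1 |
| B: hepatotoxicity G3 | 3 | 2 | 1 |

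Group A: 1 + 1 + 2 + 1 + 1 + 1 = 7. Group B: 1 + 2 + 1 + 1 = 5. Group C: 4. Total: 7 + 5 + 4 = 16.

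The count depends on convention:
- Two Group B entries are conditional: the second Day 1 to 7 thrombocytopenia event, where TG02 may still be at 150 mg, and the and/or neutropenia entry. Without them, 16 - 2 = 14.
- Four Group B entries allow the same or a reduced dose after a reduction: third grade 3 thrombocytopenia without bleeding, third grade 3 neutropenia, second grade 3 febrile neutropenia, and second other grade 4. With them, 16 + 4 = 20.

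Two Group B thrombocytopenia rows need care. The row "Second occurrence of grade 3 event with bleeding or grade 4 event occurring on Day -7 to Day -1 of cycle" writes its stop for resumption after a third event but gives no third-event action. For Day 1 to 7, the first-event row says "If TMZ is re-introduced, re-introduce TMZ and TG02 at a reduced dose", but if TMZ is stopped TG02 may stay at the same dose. A patient kept at 150 mg then has a genuine 150-to-100 reduction at the second event.

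For a patient who starts at 100 mg, 5.5.3.1 turns the first required reduction into a stop.

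**The case against.** A reader might infer that the tables contradict 5.5.3.1 in 16 places and that each such entry should become a discontinuation. The documents do not support this. Section 5.5.3.1 refers to the tables and says what to do when they require a reduction at 100 mg, so a reduced-dose entry met at 100 mg triggers that rule and does not compete with it. Thirteen of the 16 entries apply only if TG02 is re-introduced, and one can be met by lowering TMZ alone. Replacing all of them would also remove the valid Day 1 to 7 reduction described above.

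It can also be said that the neutropenia cell is coherent if *and* and *or* are read strictly: both drugs resumed means keep one, one drug resumed means stop. The and/or wording in the cell makes this possible, but nothing states it, and the thrombocytopenia cell suggests a slip instead. For grade 4 anemia, the next row and 5.5.3.1 both give a stop at the second event, so a careful site reaches the right answer.

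What stands from this side is that the practical risk is limited and item 3 is a matter of clarity. The anemia sentence still contradicts the row below it, the neutropenia cell still leaves its meaning open, and the note still omits the instruction that matters at the floor.

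**Conclusion.** The point holds as a correction to operative text. There is one contradictory grade 4 anemia row pair in each of Groups A and C, one ambiguous cell in Group B, and an asterisk note in all three groups that states the floor without the stop. The later reduced-dose entries number about 14 to 20 from a 150 mg start. That range assumes the same event recurs and depends on how optional and conditional entries are treated; the conclusion does not rest on the exact count.

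The documents give no frequency of these events at 100 or 150 mg, so the number of patients affected cannot be stated. A reader might also infer some effect on the Group C conclusion. The decision rule in 8.1.1 (at least 13 of 45 alive and progression-free at 6 months) does not use these rows and is unaffected.

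One Group B question is not settled by 5.5.3.1: it discontinues study treatment, while 5.5.3.3.2 (expansion phase) lets either agent continue when the other is stopped.

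**What to change.** 1. Delete "If TG02 has been re-introduced after a second event and the event recurs, discontinue TG02" from the grade 4 anemia rows of Groups A and C, to match Group B.
2. In Group B recurrent grade 3 neutropenia, either change the last sentence to refer to a third event, as in the thrombocytopenia cell, or state that it applies only when a single drug was resumed.
3. Reword the asterisk note in all three groups along these lines: *No reduction below 100 mg. If the table calls for a reduced dose and the patient is already at 100 mg, discontinue TG02 per 5.5.3.1. This does not apply where reduction is optional or the same dose is allowed.* In Group B, add whether TMZ may continue after such a stop.
4. Leave the remaining reduced-dose entries in place. The reworded note settles them and preserves the valid Day 1 to 7 reduction in Group B.

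The cost is editing a few table cells and one note in a single amendment. No new data, visits or patients are needed.
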